10.4.3 General guidelines for reporting adverse events

- All AEs, regardless of seriousness or relationship to IMP, spanning from the signature of the informed consent form until the end of the study as defined by the protocol for that patient, are to be recorded on the corresponding screen(s) of the e-CRF.
- Whenever possible, diagnosis or single syndrome should be reported instead of symptoms. The Investigator should specify the date of onset, intensity, action taken with respect to IMP, corrective treatment/therapy given, additional investigations performed, outcome, and his/her opinion as to whether there is a reasonable possibility that the AE was caused by the IMP or by the study procedure(s).
- The Investigator should take appropriate measures to follow all AEs until clinical recovery is complete and laboratory results have returned to normal, or until progression has been stabilized, or until death, in order to ensure the safety of the patients. This may imply that observations will continue beyond the last planned visit per protocol, and that additional investigations may be requested by the monitoring team up to as noticed by the Sponsor.
- When treatment is prematurely discontinued, the patient's observations will continue until the end of the study as defined by the protocol for that patient.
- Laboratory, vital signs or ECG abnormalities are to be recorded as AEs only if:
 - Symptomatic and/or
 - Requiring either corrective treatment or consultation, and/or
 - Leading to IMP discontinuation or modification of dosing, and/or
 - Fulfilling a seriousness criterion, and/or
 - Defined as an AESI

Instructions for AE reporting are summarized in [Table 3](#).

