11.4.3 Analyses of safety data

The summary of safety results will be presented by treatment group actually received.

All safety analyses will be performed on the safety population using the following common rules:

- The baseline value is defined generally as the last available value before the first administration of the IMP.
- For quantitative safety parameters based on central laboratory/reading measurements, descriptive statistics will be used to summarize results and change from baseline values by visit and treatment group.
- The analysis of the safety variables will be descriptive and no hypothesis testing is planned.

The following definitions will be applied to laboratory parameters, vital signs, and ECG.

- The potentially clinically significant abnormality (PCSA) values are defined as abnormal values considered medically important by the Sponsor according to predefined criteria/thresholds based on literature review and defined by the Sponsor for clinical laboratory tests, vital signs, and ECG.
- PCSA criteria will determine which patients had at least 1 PCSA during the TEAE period, taking into account all evaluations performed during the TEAE period, including unscheduled or repeated evaluations. The number of all such patients will be the numerator for the TEAE PCSA percentage.

The TEAE period is defined as the time from the first administration of the IMP up to 12 weeks (84 days) from the last dose of IMP.

Please refer to [Section 9.2](#) for the safety endpoints.

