11.4.3.1 Adverse events

Adverse event incidence tables will be provided by treatment group for all types of TEAEs: all TEAEs, all treatment emergent SAEs, all TEAEs leading to permanent treatment discontinuation, treatment-emergent AESI and TEAEs leading to death.

Analysis of TEAE

Treatment emergent adverse event incidence tables will be presented by system organ class (SOC) (sorted by internationally agreed order), high-level group term (HLGT), high level term (HLT) and preferred term (PT) sorted in alphabetical order for each treatment group, the number (n) and percentage (%) of patients experiencing at least 1 TEAE. Multiple occurrences of the same event in the same patient will be counted only once in the tables within a treatment phase. The denominator for computation of percentages is the safety population within each treatment group.

Analysis of all treatment-emergent SAEs

All treatment-emergent SAEs will be presented by primary SOC, HLT, HLT, and PT, showing number (%) of patients with at least 1 serious TEAE, sorted by SOC internationally agreed order. The other levels (HLGT, HLT, PT) will be presented in alphabetical order. A listing will be provided for all SAEs by treatment group and patient with flags indicating on-treatment status.

Analysis of all TEAEs leading to permanent treatment discontinuation

TEAEs leading to treatment discontinuation will be presented by primary SOC, HLT, HLT, and PT, showing number (%) of patients with at least 1 TEAE leading to permanent treatment discontinuation, sorted by SOC internationally agreed order. The other levels (HLGT, HLT, PT) will be presented in alphabetical order. A listing will be provided for all TEAE leading to permanent treatment discontinuation by treatment group and patient.

Analysis of treatment-emergent AESI

Treatment-emergent AESI will be presented by AESI category and PT, showing number (%) of patients with at least 1 treatment-emergent AESI, sorted by decreasing incidence of PT within each AESI category. The AESIs include, but are not limited to, the following categories and complete list of AESI categories will be provided in the statistical analysis plan: tuberculosis, anaphylaxis, hypersensitivity, and vasculitis.

Analysis of Deaths

The following deaths summaries will be generated:

- Number (%) of patients who died by study period (TEAE, on-study) summarized on the safety population by treatment received.

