2.1.5 Safety endpoints

The safety analysis will be based on the reported adverse events and other safety information, such as clinical laboratory data, vital signs, ECG.

Observation period

The observation period will be divided into 4 epochs:

- The **pre-treatment** epoch is defined as the time from the signed informed consent date up to the first administration of IMP.
- The **treatment** epoch is defined as the time from the first administration of the IMP to the last administration of the IMP + 7 days.
- The **residual treatment** epoch is defined as the time from the last administration of the IMP + 8 days to the last administration of the IMP + 84 days.

The treatment-emergent adverse event (TEAE) period will include both **treatment** and **residual treatment** epochs.

- The **post-treatment** epoch is defined as the period of time starting the day after the end of the TEAE period up to the end of the study (defined as last protocol-planned visit or last study assessment).

The on-study observation period is defined as the time from the first administration of IMP until the end of the study (defined as last protocol planned visit or last study assessment).

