2.4.5.1 Analyses of adverse events

Generalities

The primary focus of adverse event reporting will be on TEAEs. Pre-treatment and post-treatment adverse events will be described separately.

If an adverse event date/time of onset (occurrence, worsening, or becoming serious) is incomplete, an imputation algorithm will be used to classify the adverse event as pre-treatment, treatment-emergent, or post-treatment. The algorithm for imputing date/time of onset will be conservative and will classify an adverse event as treatment emergent unless there is definitive information to determine it is pre-treatment or post-treatment. Details on classification of adverse events with missing or partial onset dates are provided in [Section 2.5.3](#).

Adverse event incidence tables will present by SOC, HLTG, HLT, and PT, sorted in alphabetical order for each treatment group, the number (n) and percentage (%) of patients experiencing an adverse event. Multiple occurrences of the same event in the same patient will be counted only once in the tables within a treatment phase. The denominator for computation of percentages is the safety population within each treatment group.

Sorting within tables ensures the same presentation for the set of all adverse events within the observation period (pre-treatment, treatment-emergent, and post-treatment). For that purpose, the table of all TEAEs presented by SOC and PT sorted by the internationally agreed SOC order and decreasing frequency of PTs within SOCs will define the presentation order for all other tables unless otherwise specified. Sorting will be based on results for the experimental treatment arm.

Analysis of all treatment-emergent adverse events

The following TEAE summaries will be generated for the safety population.

- Overview of TEAEs, summarizing number (%) of patients with any
 - TEAE,
 - Serious TEAE,
 - TEAE leading to death,
 - TEAE leading to permanent treatment discontinuation.
- All TEAEs by primary SOC, HLGT, HLT, and PT, showing number (%) of patients with at least 1 TEAE sorted by the SOC internationally agreed order. The other levels (HLGT, HLT, PT) will be presented in alphabetical order.
- All TEAEs by primary SOC and PT, showing the number (%) of patients with at least 1 TEAE, sorted by the internationally agreed SOC order and by decreasing incidence of PTs within each SOC. This sorting order will be applied to all other tables, unless otherwise specified.

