- All TEAEs regardless of relationship and related to IMP by primary SOC, HLGT, HLT and PT, showing the number (%) of patients with at least 1 TEAE, sorted by the internationally agreed SOC order. The other levels (HLGT, HLT, PT) will be presented in alphabetical order.
- All TEAEs by maximal severity, presented by primary SOC and PT, showing the number (%) of patients with at least 1 TEAE by maximal severity (ie, mild, moderate, or severe), sorted by the sorting order defined above.

Analysis of all treatment emergent SAEs

- All treatment-emergent SAEs by primary SOC, HLGT, HLT, and PT, showing the number (%) of patients with at least 1 serious TEAE, sorted by the internationally agreed SOC order. The other levels (HLGT, HLT, PT) will be presented in alphabetical order.
- All treatment-emergent SAEs by primary SOC and PT, showing the number (%) of patients with at least 1 serious TEAE, sorted by the sorting order defined above.
- All treatment-emergent SAEs regardless of relationship and related to IMP, by primary SOC, HLGT, HLT, and PT, showing the number (%) of patients with at least 1 treatment-emergent SAE, sorted by the internationally agreed SOC order. The other levels (HLGT, HLT, PT) will be presented in alphabetical order.
- Listings will be provided for all SAEs by treatment arm during the TEAE period.

Analysis of all TEAEs leading to treatment discontinuation

- All TEAEs leading to treatment discontinuation, by primary SOC, HLT, HLT, and PT, showing the number (%) of patients sorted by the internationally agreed SOC order. The other levels (HLGT, HLT, PT) will be presented in alphabetical order.
- All TEAEs leading to treatment discontinuation, by primary SOC and PT, showing the number (%) of patients with at least 1 TEAE, sorted by the internationally agreed SOC order and by decreasing incidence of PTs within each SOC.
- Listing will be provided for all TEAE leading to permanent treatment discontinuation by treatment arm.

Analysis of treatment-emergent AESIs

All treatment-emergent AESIs, by AESI category and PT, showing the number (%) of patients by treatment group, sorted by decreasing incidence of PT within each AESI category. The AESIs categories and details of the MedDRA coding are provided in [Section 2.1.5.1](#).

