- Listing of all Treatment emergent AESIs experienced per patient and by treatment arm: Patient ID, AESI category, PT, time to onset of event, date of first and last IMP administration, duration, intensity, corrective treatment, seriousness, relationship to SAR.

Analysis of pre-treatment and post-treatment adverse events

If any pre-treatment or post-treatment AE lead to death or any pre-treatment AE lead to treatment discontinuation, a listing will be provided.

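### The SAP limits the SAE listing to the TEAE period, which is narrower than the protocol's wording, so some non-fatal SAEs outside that period have no specified table or listing

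*SAP*

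**What the plan says.** **SAE listing.** Protocol 11.4.3.1 ends its paragraph on SAEs with: "A listing will be provided for all SAEs by treatment group and patient with flags indicating on-treatment status". The paragraph is headed "Analysis of all treatment-emergent SAEs". SAP 2.4.5.1 has instead: "Listings will be provided for all SAEs by treatment arm during the TEAE period". The SAP sentence adds a time limit and drops the flag. SAP 1.5 says that no amendment altered the protocol's statistical section. SAP 1.6, which lists the SAP's modifications, does not mention the SAE listing.

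**Periods.** Protocol 11.4.3 runs the TEAE period from first dose "up to 12 weeks (84 days) from the last dose of IMP". SAP 2.1.5 defines a post-treatment epoch "starting the day after the end of the TEAE period up to the end of the study".

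**Collection.** SAEs are recorded from consent to end of study (Protocol 10.4.3, SAP 2.1.5.1). Protocol 10.4.3 adds: "When treatment is prematurely discontinued, the patient's observations will continue until the end of the study". Protocol 10.3.4 likewise keeps early discontinuers on the visit schedule through Week 35.

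**Events outside the TEAE period.** SAP 2.4.5.1 opens with the general statement "Pre-treatment and post-treatment adverse events will be described separately". The only output it then names for them is: "If any pre-treatment or post-treatment AE lead to death or any pre-treatment AE lead to treatment discontinuation, a listing will be provided". SAP 2.4.5.2 adds summaries and listings of deaths. The AESI listing in SAP 2.4.5.1 is limited to treatment-emergent events.

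**The concern.** The SAP defines a post-treatment epoch, and the trial collects SAEs in it, but the SAE listing stops where that epoch starts. The patients with appreciable post-treatment time are those who stopped treatment early. Many of the stopping criteria in Protocol 10.3.3 concern safety, and Protocol 10.3.4 gives safety monitoring as one reason for keeping these patients in follow-up. A late non-fatal SAE in such a patient would be collected, yet no table or listing is named to show it. If discontinuation differed between arms, the amount of follow-up without a specified output would differ too. In a trial of about 94 patients, single SAEs are read one by one, so the listing is the output that matters most here.

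**Working it through.** **Inputs**
- Planned last dose: Week 23 (Protocol 1.2, footnote c).
- End of TEAE period: last dose + 84 days (Protocol 11.4.3, SAP 2.1.5).
- End-of-study visit: Week 35, target Day 246, with the first injection on Day 1 (SAP 2.5.4, Table 3). Visit window ±2 days (Protocol 1.2, footnote a).
- Treatment discontinuation: 10% of 94 patients (Protocol 11.1, SAP 1.3).

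**Step 1: the plan's own figure.** SAP 2.1.6 places Week 35 at 12 weeks after the last injection. For a completer, the last dose is on Day 7 × 23 + 1 = 162, and 162 + 84 = 246, the Week 35 target day. The figure is reproduced. A completer has no uncovered post-treatment time, or at most 2 days if the last visit falls at the end of its window.

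**Step 2: early discontinuers.** With the last dose at Week w:
- day of last dose = 7w + 1
- end of TEAE period = 7w + 1 + 84 = 7w + 85
- uncovered days to Day 246 = 246 - (7w + 85) = 161 - 7w, which is 23 - w weeks

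| Week of last dose | TEAE period ends on day | Days outside the listing |
|---|---|---|
| 0 | 85 | 161 |
| 4 | 113 | 133 |
| 8 | 141 | 105 |
| 12 | 169 | 77 |
| 16 | 197 | 49 |
| 20 | 225 | 21 |
| 22 | 239 | 7 |
| 23 (completer) | 246 | 0 |

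**Step 3: total.** Assume that last doses are spread evenly over Weeks 0 to 22 and that every discontinuer stays to Week 35. The documents give neither.
- Mean per discontinuer: 161 - 7 × 11 = 84 days.
- At 10%: 9.4 × 84 = 789.6 patient-days; divided by 365.25, 2.2 patient-years.
- Planned follow-up: 94 × 246 = 23,124 patient-days, so the share is 789.6 / 23,124 = 3.4%.
- Range if 5% or 20% discontinue (my assumption): 4.7 × 84 / 365.25 = 1.1 and 18.8 × 84 / 365.25 = 4.3 patient-years.
- Upper limit at 10%, all stopping after the first dose: 9.4 × 161 / 365.25 = 4.1 patient-years.

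**Step 4: which named output covers which SAE**

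| SAE | Named output in SAP 2.4.5.1 and 2.4.5.2 |
|---|---|
| In the TEAE period | TEAE and SAE tables, SAE listing |
| Post-treatment, fatal | Listing of AEs leading to death; death outputs |
| Post-treatment, non-fatal | None named |
| Pre-treatment, fatal or leading to treatment discontinuation | Listing |
| Pre-treatment, other | None named |

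**The case against.** **The SAP promises a description.** A reader might infer that the uncovered SAEs will appear nowhere. The documents do not support that. SAP 2.4.5.1 says that pre- and post-treatment AEs will be described separately, and its sorting rule for tables mentions both periods. Protocol 10.5 commits the sponsor to reporting all safety observations in the study report, and Protocol 10.7 says much the same. What remains is that no table or listing is specified, and that the SAP's paragraph on these events is narrower than its own general statement.

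**The protocol sentence can be read narrowly.** It stands under a treatment-emergent heading. It is also tempting to argue that an on-treatment flag makes sense only if the listing extends beyond the TEAE period. That does not follow. SAP 2.1.5 divides the TEAE period into a treatment epoch (to last dose + 7 days) and a residual epoch, and SAP 2.4.4.1.3 ends the on-treatment period at last dose + 7 days. SAP 2.1.5.2 uses the term differently, calling deaths anywhere in the TEAE period on-treatment. The flag therefore settles nothing. The wide reading rests on the literal reference to all SAEs; the neighbouring paragraph on discontinuations limits its listing to TEAEs in so many words.

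**The period at issue is late and small.** With a half-life of about 15 days (Protocol section 4), 84 days is 84 / 15 = 5.6 half-lives. That is a fair reason to base the tables on the TEAE period, but it does not explain why the listing should stop there. SAEs with incomplete onset dates default to treatment-emergent (SAP 2.4.5.1, 2.5.3), so only those clearly dated outside the period are affected. Patients may also withdraw from the study (Protocol 10.3.5), which shortens the uncovered time. SAE collection, expedited reporting and data monitoring committee review go on regardless. All of this stands and limits the importance of the point.

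**Conclusion.** The concern holds in a limited form. The SAP's SAE listing is narrower than the literal wording of Protocol 11.4.3.1, and SAP 1.6 does not declare the difference. Within SAP 2.4.5.1, the general promise to describe pre- and post-treatment AEs and the single listing that follows do not agree. As a result, non-fatal SAEs clearly dated after last dose + 84 days, and non-fatal pre-treatment SAEs that do not lead to discontinuation, have no specified table or listing.

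The post-treatment part is up to 23 - w weeks per early discontinuer still in follow-up. It comes to about 2 patient-years (about 3% of planned follow-up) under 10% discontinuation, an even spread of stopping times and full follow-up. This measures time, not missed events: the documents give no SAE rate, so no number of events can be derived. Nor do they show that discontinuation will differ between arms.

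The primary analysis, the other efficacy analyses and the TEAE tables are unaffected. The change is still worth making, because it completes the SAE reporting for patients who stopped early.

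**What to change.** In SAP 2.4.5.1, replace the SAE listing sentence with a listing of all SAEs collected from informed consent to end of study, by arm and patient, with a flag for epoch or on-treatment status. If on-treatment status is used, define it, because SAP 2.1.5.2 and 2.4.4.1.3 use the term differently. Then align the paragraph on pre- and post-treatment AEs with the general statement earlier in the section, naming the output that is meant. If the sponsor prefers to keep the listing to the TEAE period, SAP 1.6 should say so and the SAP should name where the remaining SAEs will be shown.

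The time span and an epoch flag are my proposal; Protocol 11.4.3.1 does not spell them out. A table of post-treatment SAEs by preferred term and arm would be an optional addition, which the protocol does not require.

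The cost is a small text change and one wider listing from data already collected. Sample size, power and all efficacy outputs stay as they are.

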2.4.5.2 Deaths

The following summaries of deaths will be generated for the safety population by treatment group.

- Number (%) of patients who died by study period (on-study, on-treatment, post-study).
- Deaths in non-randomized patients or randomized but not treated patients.
- TEAEs leading to death (death as an outcome on the adverse event case report form page as reported by the Investigator) by primary SOC, HLT, HLT, and PT showing number (%) of patients sorted by internationally agreed SOC order, with HLT, HLT, and PT presented in alphabetical order within each SOC.
- Listings of deaths will be provided.

2.4.5.3 Analyses of laboratory variables

The summary statistics (including number, mean, median, standard deviation, minimum and maximum) of all laboratory variables (central laboratory values and changes from baseline) will be calculated for each visit (baseline and post-baseline time points) and presented by treatment group. This section will be organized by biological function as specified in [Section 2.1.5.3](#).

For parameters creatinine, glucose, neutrophils, monocytes, basophils, eosinophils and bicarbonate, the last on-treatment and worst on-treatment value will also be provided.

The incidence of PCSAs (list provided in [Appendix A](#)) at any time during the TEAE period will be summarized by biological function and treatment group whatever the baseline level and/or according to the following baseline status categories:

- Normal/missing.
- Abnormal according to PCSA criterion or criteria.

For parameters for which no PCSA criteria are defined, similar table(s) using the normal range will be provided.

Listing will be provided with flags indicating the out of range values as well as PCSA values.

Drug-induced liver injury

The liver function tests, namely AST, ALT, alkaline phosphatase, and total bilirubin, are used to assess possible drug-induced liver toxicity. The proportion of patients with PCSA values at any post-baseline visit by baseline status will be displayed by treatment group for each parameter.

A graph of distribution of peak values of ALT versus peak values of total bilirubin will also be presented. Note that the ALT and total bilirubin values are presented on a logarithmic scale. The graph will be divided into 4 quadrants with a vertical line corresponding to $3 \times \text{ULN}$ for ALT and a horizontal line corresponding to $2 \times \text{ULN}$ for total bilirubin.

The normalization (to $\leq 1 \times \text{ULN}$ or return to baseline if baseline $>\text{ULN}$) of elevated liver function tests will be summarized for each parameter by categories of elevation ($3 \times$, $5 \times$, $10 \times$, $20 \times \text{ULN}$ for ALT and AST, $1.5 \times \text{ULN}$ for alkaline phosphatase, and $1.5 \times$ and $2 \times \text{ULN}$ for total bilirubin), with the following categories of normalization: no worsening as compared to the baseline PCSA status, returned to baseline PCSA status before last IMP dose, returned to baseline PCSA status after last IMP dose, never returned to baseline PCSA status, no assessment after the worst on-treatment value. Note that a patient will be counted only under the maximum elevation category.

The incidence of liver-related adverse events will be summarized by treatment group. The selection of PTs will be based on the hepatic disorder SMQ.

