11.4.3.3 Potential drug-induced liver injury

The liver function tests, namely ALT, AST, ALP and total bilirubin (TBILI), are used to assess possible drug induced liver toxicity. The proportion of patients with PCSA values at any post-baseline visit by baseline status will be displayed by treatment group for each parameter.

A graph of distribution of peak values of ALT versus peak values of TBILI will be presented. Note that the ALT and TBILI values are presented on a logarithmic scale. The graph will be divided into 4 quadrants with a vertical line corresponding to 3 x ULN for ALT and a horizontal line corresponding to 2 x ULN for TBILI.

The normalization (to ≤ 1 x ULN or return to baseline if baseline $>$ ULN) of elevated liver function tests will be summarized by categories of elevation (3 x ULN, 5 x ULN, 10 x ULN,

20 x ULN for ALT and AST, 1.5 x ULN for ALP, and 1.5 x ULN and 2 x ULN for TBILI), with the following categories of normalization: never normalized, normalized after permanent discontinuation of study drug. Note that a patient will be counted only under the maximum elevation category (1-3 x ULN, 3-5 x ULN, 5-10 x ULN, 10-20 x ULN, >20 x ULN).

The incidence of liver-related AEs will be summarized by treatment group. The selection of PTs will be based on standardized Medical Dictionary for Regulatory Activities (MedDRA) query (SMQ) Hepatic disorder.

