Appendix K General guidance for the follow-up of laboratory abnormalities by Sanofi

NEUTROPENIA

[figure not shown]

Note:

- The procedures described in the above flowchart are to be discussed with the patient only in case the event occurs. If applicable (according to local regulations), an additional consent (e.g., for HIV testing) will only be obtained in the case the event actually occurs.
- For individuals of African descent, the relevant value of concern is <1000/mm³

Neutropenia is to be recorded as an AE only if at least 1 of the criteria listed in the general guidelines for reporting AEs in [Section 10.4.3](#) is met.

[figure not shown]
THROMBOCYTOPENIA

Note:

The procedures above flowchart are to be discussed with the patient only in case described in the the event occurs. If applicable (according to local regulations), an additional consent (e.g., for HIV testing) will only be obtained in the case the event actually occurs.

Thrombocytopenia is to be recorded as an AE only if at least 1 of the criteria listed in the general guidelines for reporting AEs in [Section 10.4.3](#) is met.

[figure not shown]

- *If unable to retest in 72 hours, use original lab results to decide on further reporting/monitoring/discontinuation.
- Note:
- “Baseline” refers to ALT sampled at baseline visit; or if baseline value unavailable, to the latest ALT sampled before the baseline visit. The algorithm does not apply to the instances of increase in ALT during screening.

See [Section 10.4](#) for guidance on safety reporting.

[figure not shown]
- Normalization is defined as \leq ULN or baseline value, if baseline value is $>$ ULN.

ACUTE RENAL FAILURE

Acute renal failure is to be recorded as an AE only if at least 1 of the criteria listed in the general guidelines for reporting AEs in [Section 10.4.3](#) is met.

SUSPICION OF RHABDOMYOLYSIS

Suspicion of rhabdomyolysis is to be recorded as an AE only if at least 1 of the criteria in the general guidelines for reporting AEs in [Section 10.4.3](#) is met.

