Appendix A Potentially clinically significant abnormalities criteria

CRITERIA for POTENTIALLY CLINICALLY SIGNIFICANT ABNORMALITIES for Phase 2/3 studies (oncology excepted)

Parameter	PCSA	Comments
Clinical Chemistry		
ALT	By distribution analysis: >3 ULN >5 ULN >10 ULN >20 ULN	Enzymes activities must be expressed in ULN, not in IU/L. Concept paper on DILI - FDA draft Guidance Oct 2007. Internal DILI WG Oct 2008. Categories are cumulative. First row is mandatory. Rows following one mentioning zero can be deleted.
AST	By distribution analysis: >3 ULN >5 ULN >10 ULN >20 ULN	Enzymes activities must be expressed in ULN, not in IU/L. Concept paper on DILI - FDA draft Guidance Oct 2007. Internal DILI WG Oct 2008. Categories are cumulative. First row is mandatory. Rows following one mentioning zero can be deleted.
Alkaline Phosphatase	>1.5 ULN	Enzymes activities must be expressed in ULN, not in IU/L. Concept paper on DILI - FDA draft Guidance Oct 2007. Internal DILI WG Oct 2008.
Total Bilirubin	>1.5 ULN >2 ULN	Must be expressed in ULN, not in μ mol/L or mg/L. Categories are cumulative. Concept paper on DILI - FDA draft Guidance Oct 2007. Internal DILI WG Oct 2008.
Conjugated Bilirubin	>35% Total Bilirubin and TBILI>1.5 ULN	Conjugated bilirubin dosed on a case-by-case basis.
ALT and Total Bilirubin	ALT >3 ULN and TBILI >2 ULN	Concept paper on DILI - FDA draft Guidance Oct 2007. Internal DILI WG Oct 2008. To be counted within a same treatment phase, whatever the interval between measurement.

**CRITERIA for POTENTIALLY CLINICALLY SIGNIFICANT ABNORMALITIES
for Phase 2/3 studies (oncology excepted)**

Parameter	PCSA	Comments
CPK	>3 ULN >10 ULN	FDA Feb 2005. Am J Cardiol April 2006. Categories are cumulative. First row is mandatory. Rows following one mentioning zero can be deleted.
CLcr (mL/min) (Estimated creatinine clearance based on the Cokcroft-Gault equation)	<15 (end stage renal disease) ≥15 - <30 (severe decrease in GFR) ≥30 - <60 (moderate decrease in GFR) ≥60 - <90 (mild decrease in GFR) ≥90 (normal GFR)	FDA draft Guidance 2010. Pharmacokinetics in patients with impaired renal function-study design, data analysis, and impact on dosing and labeling.

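### The SAP's liver table defines normalization as at or below 1×ULN (or back to a raised baseline) but sorts patients by return to baseline PCSA status, so values up to 3×ULN for ALT and AST can be shown as returned

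*SAP*

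**What the plan says.** The liver-injury part of SAP 2.4.5.3 announces that normalization "of elevated liver function tests will be summarized for each parameter by categories of elevation". In the same sentence it explains normalization as a value at or below 1×ULN, or a return to baseline where baseline was above ULN.

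The rows that follow are introduced "with the following categories of normalization: no worsening as compared to the baseline PCSA status", and continue "returned to baseline PCSA status before last IMP dose, returned to baseline PCSA status after last IMP dose". Next comes a row for patients who never got back to that status, and a last row covers patients with no measurement after their worst on-treatment value. No row uses the 1×ULN criterion.

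Protocol 11.4.3.3 plans the same table under the same definition, but with rows that match it: "with the following categories of normalization: never normalized, normalized after permanent discontinuation of study drug". It also lists 1 to 3×ULN as a category of elevation. Protocol Appendix K, in its guidance on following laboratory abnormalities, takes normalization to be at or below "ULN or baseline value, if baseline value is" above ULN.

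For PCSA status, SAP Appendix A gives for ALT and for AST "By distribution analysis: >3 ULN >5 ULN >10 ULN >20 ULN". For alkaline phosphatase the level is above 1.5×ULN, and for total bilirubin above 1.5 and above 2×ULN. SAP 2.4.5.3 splits baseline status in two: normal or missing, and "Abnormal according to PCSA criterion or criteria".

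SAP 1.6, which lists the changes made in the SAP, does not mention that the rows differ from the protocol's.

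**The concern.** Normalization and return to baseline PCSA status are different events. The first asks whether the test is back in the normal range, or back to where the patient started. The second asks only whether the value has dropped out of the range that the sponsor flags as potentially significant. For ALT and AST that range begins above 3×ULN, so a residual elevation of nearly three times the normal limit satisfies the second and fails the first.

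This table is where a reader looks to see whether liver elevations went away, and whether they did so before or after dosing stopped. ALT above 3×ULN is an adverse event of special interest in Protocol 10.4.1.3. If the rows record the weaker event under a heading that promises the stronger one, recovery looks more complete than it was. It can also look earlier: a patient who drops below 3×ULN before the last dose, and reaches the normal range only afterwards, goes in the before-last-dose row.

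**Working it through.** The plan states no figure to reproduce here. The check applies the two rules to the same patients and finds where they disagree.

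**Inputs**
- Stated criterion: SAP 2.4.5.3 and Protocol 11.4.3.3.
- PCSA threshold T, in ×ULN: 3 for ALT and AST, 1.5 for alkaline phosphatase, 1.5 or 2 for bilirubin (SAP Appendix A).
- Baseline: E 23 excludes ALT or AST above 2×ULN at screening, and SAP 2.5.3 groups a missing baseline with normal. Nearly every patient is therefore non-PCSA at baseline for ALT and AST. E 23 sets no limit for alkaline phosphatase or bilirubin, so for those tests the argument covers only patients who are in fact at or below T at baseline.

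**Rules**, with B the baseline value and L the last value, both in ×ULN:
- Stated criterion: normalized if L ≤ 1, or if B > 1 and L ≤ B.
- SAP rows, for a patient with B ≤ T: returned if L ≤ T.

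**Illustrative patients** (chosen values, not trial data)

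| Test (T) | Baseline / peak / last | Normalized | Returned |
|---|---|---|---|
| ALT or AST (3) | 0.8 / 8 / 0.9 | yes | yes |
| | 0.8 / 8 / 1.5 | no | yes |
| | 0.8 / 8 / 2.9 | no | yes |
| | 0.8 / 8 / 3.0 | no | yes |
| | 0.8 / 8 / 3.1 | no | no |
| | 1.8 / 8 / 1.8 | yes | yes |
| | 1.8 / 8 / 2.9 | no | yes |
| | 2.0 / 22 / 3.0 | no | yes |
| Alkaline phosphatase (1.5) | 0.8 / 2.5 / 1.4 | no | yes |
| Bilirubin (1.5) | 0.8 / 2.5 / 1.4 | no | yes |
| Bilirubin (2) | 0.8 / 2.5 / 1.9 | no | yes |

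**Where they disagree.** The rules differ exactly when max(1, B) < L ≤ T. For ALT or AST with baseline 0.8, that is any last value above 1 and up to 3×ULN. With baseline 1.8, it is above 1.8 and up to 3×ULN.

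**Direction.** If B ≤ T, a patient who meets the stated criterion has L ≤ 1 or L ≤ B, and in either case L ≤ T. Normalized therefore implies returned, but not the reverse. The two returned rows taken together can only be too large, and the never-returned row too small.

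**The case against.** The best defence is that the parenthesis gives the criterion and the rows add only timing relative to the last dose. That does not fit the text: three of the rows name PCSA status as the thing returned to or not returned to, and the no-worsening row names it too. A softer version is that normal, in the baseline split, might mean at or below ULN. The split sets normal or missing against abnormal by PCSA criterion, so a value of 2×ULN falls on the normal side. If something else was meant, the SAP needs to say so.

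It is also fair to say that the analysis is descriptive and that individual data are not lost. SAP 2.4.5.3 provides a listing that flags out-of-range and PCSA values, and SAP 2.4.5.1 lists events of special interest with their duration. This limits the consequence, but a listing does not correct a by-arm summary. The by-visit summaries help little with recovery after dosing, because SAP 2.4.5 confines them to samples up to the day of the last dose.

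Appendix K is guidance for follow-up, not a tabulation rule. It supports the meaning of the word, but the comparison that counts is SAP 2.4.5.3 with Protocol 11.4.3.3.

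Some stronger readings are tempting, and the documents do not support them:
- *Every ALT or AST value between 1 and 3×ULN is misplaced.* The baseline clause rules this out: baseline 1.8 with last value 1.8×ULN is correctly placed under both rules.
- *E 23 makes all patients non-PCSA at baseline for all four tests.* It limits only ALT and AST, and only at screening.
- *The table calls unresolved injury resolved.* No row uses that word; the fault is that return to PCSA status is presented as a category of normalization.
- *A definite number of patients is affected.* The documents give no rate of liver elevations.

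**Conclusion.** The point holds as an internal contradiction in SAP 2.4.5.3 and an undeclared departure from the protocol's rows. For a patient who is non-PCSA at baseline, returned means a fall to 3×ULN or less for ALT and AST, 1.5×ULN or less for alkaline phosphatase, and 1.5 or 2×ULN or less for bilirubin. Patients whose last value lies above max(1×ULN, baseline) and at or below that threshold are shown as returned in a table of normalization.

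The direction is certain for these patients; the number is unknown. The conclusion assumes that status is judged at the lowest PCSA level for ALT and AST. The levels are cumulative and the SAP does not say which one applies within each elevation category. A reader might infer that each category uses its own threshold, which would widen the gap, but nothing in the SAP establishes that.

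This concerns a descriptive safety table. It does not touch the primary endpoint, and it calls for no change to clinical management.

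**What to change.** Define the rows in SAP 2.4.5.3 by the criterion the sentence already states:

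1. no worsening versus baseline;
2. normalized (at or below 1×ULN, or at or below baseline if baseline was above ULN) before the last dose;
3. normalized after the last dose;
4. never normalized;
5. no measurement after the worst on-treatment value.

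Keep the first row separate and assign it first. Without it, a patient whose alkaline phosphatase sits at 1.8×ULN throughout, which E 23 permits, would enter the elevation category above 1.5×ULN and be counted as normalized without ever having changed.

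Alternatively, keep the PCSA rows, label them as return to baseline PCSA status rather than normalization, and add normalization rows by the stated criterion. Either way, list the departure from the protocol's rows in SAP 1.6.

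The cost is a wording change and one extra derivation. The recovery figures may look slightly less favourable.
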